8.1.5.1 BASELINE ASSESSMENTS

Participants will be prompted by the CareQOL after registration to complete the baseline HRQOL assessments. Administration time is 10-15 minutes.

8.1.5.2 DAILY ASSESSMENTS

Participants will be prompted by the CareQOL app to complete a brief 3-item assessment once per day during the run-in and six-month (180 day) home monitoring periods. These questions will be answered directly on the app and involve <1 minute administration time in total. The daily assessments will include:

- TBI-CareQOL Caregiver Strain – single-item assessment to evaluate self-reported caregiver strain. The individual items that are administered each day will vary.
- PROMIS Anxiety – single item assessment to evaluate self-reported anxiety. The individual items that are administered each day will vary.
- PROMIS Depression – single item assessment to evaluate self-reported depression. The individual items that are administered each day will vary.

8.1.5.3 MONTHLY ASSESSMENTS

Participants will be prompted by the CareQOL app to complete a series of self-report surveys at the end of each month (day 30, 60, 90, 120, 150, 180) during the 6-month (180 day) home monitoring period. They will also complete a post-intervention/app feasibility survey at the end of month 6 (day 180). These surveys will be answered directly on the CareQOL app and/or by interview, and should take ~10-15 minutes to complete.

- Study Feasibility: At the 6-month (180 day) assessment only, participants will complete a Study Feasibility survey to assess the experience of the participant with the study methodology and technology, including the CareQOL app, Fitbit®, and the JITAi. Administration time is 5 minutes.

Additionally, participants will update their medical history, medications, therapies, and COVID history and be queried about AEs at the end of month 3 (day 90) and month 6 (day 180).

- Medical History, Medications, Treatments, COVID Questionnaire. Participants will update their medical history and current treatments/management strategies (medication and non-medication – e.g., exercise, mindfulness) and COVID history. Administration time for this assessment is 10 minutes
- Adverse Events. Participants will be asked about any changes in mental or physical health. Administration time is 5 minutes.

8.1.5.4 FOLLOW-UP ASSESSMENTS

Participants will be prompted by the CareQOL app to complete a series of self-report surveys at +3-months (270 days) and +6-months (360 days) follow-up. As with the monthly surveys, responses will be directly entered into the CareQOL app and/or by interview and should take ~10-15 minutes to complete. Additionally, participants will update their medical history, medications, treatments and COVID history and be queried about AEs at these time points.

8.1.6 OPTIONAL SEMI-STRUCTURED INTERVIEW (Added in protocol version 4.0)

Participants who have not completed the main caregiver study at the time of protocol version 4.0 IRB approval (~March 2023) may be invited to complete an **optional**, in-depth semi-structured interview that will assess participants' experiences and perceptions of the caregiver study, particularly their experiences and perceptions of the CareQOL app. Additionally, participants that are in the intervention group will also be asked about the intervention messages that they received from the CareQOL app. The interview will be conducted via Zoom, audio-recorded and last for 45-60 minutes. The interview will be conducted after the 6-month home monitoring period is completed. The data collected from this interview will be used to improve the CareQOL app and inform study design for future studies.

Participants who choose to complete this optional interview will be required to provide separate informed consent for this portion of the study, and participants will receive \$30 for completing the interview. The audio-recording of the interview will be transcribed and analyzed using qualitative analysis software (e.g., NVivo).

8.2 ADVERSE EVENTS AND SERIOUS ADVERSE EVENTS

8.2.1 DEFINITION OF ADVERSE EVENTS

The U-M IRBMED definition of an adverse event will be used for this study. The definition can be found at <https://az.research.umich.edu/medschool/glossary> and is below:

An adverse event (AE) is any experience or abnormal finding that has taken place during the course of a research project and was harmful to the subject participating in the research, or increased the risks of harm from the research, or had an unfavorable impact on the risk/benefit ratio. The event may or may not be caused by an intervention. Adverse events also include psychological, social, emotional or financial harms.

8.2.2 DEFINITION OF SERIOUS ADVERSE EVENTS

The U-M IRBMED definition of a serious adverse event (SAE) will be used for this study. The definition can be found at <https://az.research.umich.edu/medschool/glossary> and is below:

A serious adverse event (SAE) is any adverse experience occurring at any dose or level of participation that results in any of the following outcomes:

- Results in death,
- Is life-threatening,
- Requires inpatient hospitalization or prolongation of existing hospitalization,
- Results in persistent or significant disability/incapacity, or
- Is a congenital anomaly/birth defect.

8.2.3 CLASSIFICATION OF AN ADVERSE EVENT

NIH Behavioral and Social Intervention Clinical Trial Protocol Template v3.0 - 20180827

8.2.3.1 SEVERITY OF EVENT

All AEs will be assessed by the principal investigator, and/or if necessary, a study co-investigator or the study's independent safety monitor.

The following guidelines will be used to describe severity.

- **Mild** – Events require minimal or no treatment and do not interfere with the participant's daily activities.
- **Moderate** – Events result in a low level of inconvenience or concern with the therapeutic measures. Moderate events may cause some interference with functioning.
- **Severe** – Events interrupt a participant's usual daily activity and may require systemic drug therapy or other treatment. Severe events are usually potentially life-threatening or incapacitating. Of note, the term "severe" does not necessarily equate to "serious".

8.2.3.2 RELATIONSHIP TO STUDY INTERVENTION/EXPERIMENTAL MANIPULATION

All adverse events (AEs) will have their relationship to study procedures, including the intervention, assessed by an appropriately-trained investigator based on temporal relationship and his/her clinical judgment. All AEs will be categorized according to the likelihood that they are related or not related to the study intervention.

- **Related (Possible, Probable, Definite)**
 - The event is a known or suspected effect of the intervention or research procedures (e.g., listed in the protocol documents including, consent, publications, etc.)
 - There is at least a reasonable temporal relationship between the intervention or procedure and the event onset
 - The event abates when the intervention is discontinued
 - The event reappears upon a re-challenge with the intervention
 - The event includes data that was collected solely for research purposes
 - The event included disturbing or upsetting questions asked solely for research purposes
- **Not Related (Unlikely, Not Related)**
 - The event is NOT a known or suspected effect of the study intervention or procedures
 - The event is readily explained by characteristics of the study population
 - There is no temporal relationship between the intervention and event onset
 - An alternate etiology has been established

8.2.3.3 EXPECTEDNESS

An investigator with appropriate expertise will be responsible for determining whether an adverse event (AE) is expected or unexpected. An event that is expected has been addressed or described in one or more of the following: Informed consent document for this study, IRB application for this study, grant application or study agreement, protocol or procedures for this study, ISR Reports, published literature,

other documentation, or characteristics of a study population. An AE will be considered unexpected if the nature, severity, or frequency of the event is not consistent with the risk information described.

8.2.4 TIME PERIOD AND FREQUENCY FOR EVENT ASSESSMENT AND FOLLOW-UP

The occurrence of an AE or SAE may come to the attention of the study team via spontaneous report or formal assessment, where participants will be asked to describe any physical or mental health worries/concerns since the last check-in (see SOA for time points). Regardless of the reporting mechanism, the study team will probe any concerns to get additional information and determine if it is an adverse event. Details will be documented in the participant study record.

Any side effects that are determined to be adverse events related to study participation will be documented on the study adverse event form in the study REDCap database and followed until resolution.

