- ii. Fatigue, Frustration, Stress and/or Anxiety. It is possible that participants may experience fatigue, frustration or feel inconvenienced when completing the self-report surveys, when receiving the personalized interventions from the CareQOL app or from wearing the Fitbit®. Participants may also feel fatigue, stress and/or anxiety related to completing the study activities. Participants will be instructed that they can skip any questions that make them feel uncomfortable, and if they receive an app alert when it isn't convenient for them, they can wait and open the app when it is more convenient.
- iii. Skin Irritation. Some participants may get skin irritation from wearing the Fitbit®. Participants will be instructed to remove the device if this occurs and to contact the study team. Their band may be swapped out for a different type of wristband if they experience irritation. We offer a wide variety of wristbands to help make the Fitbit® as comfortable as possible.

To minimize the potential for risks, participants will be briefed in detail as to what they will experience throughout the study. All participants are informed that they may terminate participation from the study at any time without penalty.

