8.2.5 MULTI-SITE ADVERSE EVENT REPORTING

For this study, only related adverse events will be reported. Adverse events will be reported to U-M IRBMED and NINR using the standard IRBMED reporting schedule: (<https://az.research.umich.edu/medschool/guidance/adverse-event-reporting>). The U-M IRBMED reporting schedule is dependent on the severity of the event, and whether such adverse events were expected. Any serious adverse events will be reported to the ISM, U-M IRBMED and NINR as soon as possible but not later than 7 days of learning of the event. Non-threatening potentially serious adverse events that are causally related to the research will be reported within 14 days of learning of the event to the ISM, U-M IRBMED and NINR.

Sites will report study-related adverse events using the adverse event form in the REDCap study database promptly. In the case of a serious adverse event, the project PI and project manager should be notified by email or phone as soon as possible but not later than 7 days of learning of the event. Adverse events will be discussed at investigator and project staff meetings.

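### AE-form entry and reporting are required only for adverse events judged related, so the form data depend on individual attribution, and Section 9 plans no AE summary by arm

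*Combined protocol and SAP*

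**What the plan says.** Section 8.2.1 defines an adverse event without requiring that the intervention caused it, and includes psychological and emotional harm. Section 8.2.4 has staff probe every concern and keep the details in the participant study record. It then says: "Any side effects that are determined to be adverse events related to study participation will be documented on the study adverse event form". Section 8.2.5 adds "For this study, only related adverse events will be reported" and "Sites will report study-related adverse events using the adverse event form in the REDCap study database promptly".

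Section 8.2.3.2 assigns relatedness by timing and clinical judgment. One bullet for the related class is "The event is a known or suspected effect of the intervention or research procedures". Two bullets for the not-related class are "The event is NOT a known or suspected effect of the study intervention or procedures" and "The event is readily explained by characteristics of the study population". The protocol does not say whether one bullet or all must be met, or which class prevails if bullets in both lists apply. On who assesses, 8.2.3.1 says "All AEs will be assessed by the principal investigator, and/or if necessary, a study co-investigator" and also names the independent safety monitor.

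Section 2.3.1 lists among the study risks: "Participants may also feel fatigue, stress and/or anxiety related to completing the study activities".

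Section 9 covers hypotheses, sample size, populations, primary and secondary endpoints and baseline descriptives. It contains no adverse-event summary.

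**The concern.** A randomised control arm allows study-induced distress to be separated from the background distress of caregiving without a causal verdict on each event: all events are counted and the arms compared. Here the causal verdict comes first and decides which non-serious events must be on the form.

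That verdict is hardest for the events this trial expects. Fatigue, stress and anxiety are named as risks of taking part, and the synopsis also names them as common consequences of being a care partner. Two careful assessors could class the same event differently. If events classed as not related are not entered, the form data cannot show how often that class was used. What is at stake is a ready AE count that does not depend on attribution, and its comparison by arm. No efficacy claim is at stake.

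**Working it through.** The documents give no AE rate and no share of AEs classed as not related, so there is no plan figure to reproduce. The check is mainly textual.

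**Step 1. Does the rule filter on attribution?** Under 8.2.1 an unrelated harm is still an AE. Sections 8.2.4 and 8.2.5 require form entry for related AEs and name no form entry for the rest. Section 8.2.5 limits reporting to related AEs. So yes, for non-serious events.

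**Step 2. Can one event fit both lists?**

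| Text | Effect for a fatigue, stress or anxiety event |
|---|---|
| 2.3.1 lists it as a study risk | Meets the related bullet on known or suspected effects; fails the matching not-related bullet |
| Synopsis describes it as common in care partners | Can meet the not-related bullet on population characteristics |
| Related class covers possible, probable and definite | Leans towards entry on the form |
| No any/all or precedence rule | Judgment decides |

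The text permits either class. It does not oblige the assessor to choose not related.

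**Step 3. What else captures these events?** AE queries are scheduled for all participants at days 90, 180, 270 and 360 (8.1.5 table, 8.1.5.3, 8.1.5.4). PROMIS Anxiety, PROMIS Fatigue and NIH Toolbox Perceived Stress are collected at baseline, monthly and at both follow-ups. Anxiety is a secondary endpoint compared by arm (9.4.3).

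**Step 4. How far could the form count depend on attribution?** Illustration only: the 10% event rate and the shares are assumptions, and 280 is the enrolment ceiling. Participants with such an event = 280 × 0.10 = 28. Participants on the form = 28 × share classed related.

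| Share classed related | On the form | Not on the form |
|---|---|---|
| 100% | 28 (10.0%) | 0 |
| 75% | 21 (7.5%) | 7 |
| 50% | 14 (5.0%) | 14 |
| 25% | 7 (2.5%) | 21 |

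At a 50% share, an assumed 5% rate gives 14 participants with 7 on the form, and a 20% rate gives 56 with 28 on the form. The last column includes events correctly classed as not related. It shows sensitivity to attribution and does not estimate harms missed.

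**Step 5. What could a by-arm table show?** With equal observed proportions p in two arms of size n, and Wilson limits l and u for each arm, the Newcombe 95% interval for the risk difference is ±√[(p − l)² + (u − p)²].

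For p = 0.10 and n = 140, l = 0.0605 and u = 0.1609, so the half-width is √(0.0395² + 0.0609²) = 0.0726.

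| Assumed rate in each arm | 140 per arm | 119 per arm (140 × 0.85; 15% attrition, 9.2) |
|---|---|---|
| 5% | ±5.6 points | ±6.1 points |
| 10% | ±7.3 points | ±7.9 points |
| 20% | ±9.4 points | ±10.2 points |

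Such a table describes; it cannot rule out a moderate difference.

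**The case against.** The strongest reply is that the ambiguity lies in symptom names more than in events. Section 2.3.1 speaks of distress from doing the study; the synopsis speaks of distress from the caregiver role. Timing and trained judgment are meant to separate the two, and an event rightly classed as not related is not a missed study harm. This stands in part: it is why no under-count can be asserted. It does not make the form data independent of that judgment.

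Second, the form sentences require entry of related events without forbidding other entries, and neither the form nor the manual of procedures is in the documents. The form may already hold a relatedness field. This stands too. The point concerns what the protocol requires.

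Third, the information is largely held elsewhere: study records, scheduled queries, symptom scores and an annual safety monitor report. This keeps the consequence small. But arm means are not event counts, the monitor's report is not specified by arm, and no tabulation of study-record entries is planned.

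A reader might go further and infer that listed harms are being dropped, or that the filter works differently in the two arms and biases a safety comparison. The documents support neither. The rule permits omission without requiring it. The protocol does not say whether the assessor knows the arm, and nothing shows attribution differing by arm. Nor is there ground to infer that serious events escape: the 7-day rule in 8.2.5 covers any serious event and is not worded as conditional on relatedness.

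**Conclusion.** The point holds as a minor design matter. Required AE-form entry, and reporting of non-serious events, depend on individual attribution; the criteria leave some expected events to judgment; and no AE summary by arm is planned. The size of any under-count is unknown and may be zero. The figures of 0 to 21 participants off the form rest on an assumed 10% rate and assumed classification shares, and they count correct not-related decisions along with incorrect ones. Section 2.3.3 describes the risks as minimal, serious-event reporting stands as written, and the primary and secondary efficacy results are unaffected. What is missing is a ready AE count that does not depend on attribution, shown by arm.

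**What to change.** - **Section 8.2.4:** enter every event determined to be an AE on the REDCap AE form whatever its attribution, with relatedness recorded as a field. Cover all types, including skin irritation, which 2.3.1 also lists.
- **Limits to keep:** follow-up until resolution, and IRB and NINR reporting of non-serious events, stay confined to related events. Say so explicitly. Section 8.2.4 now ties follow-up to form entry, and without this limit the duty would extend to chronic caregiver stress that may never resolve. Leave serious-event reporting as it is.
- **Participants already on study:** version 4.0 (February 2023) was written with participants in progress. Either complete the form for them from existing study records, or state the date from which capture changed, so that mixed capture is visible.
- **Section 9:** add one descriptive table of participants with each AE by randomised arm, overall and split by attribution, with no test.

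The criteria in 8.2.3.2 can stay, because attribution would no longer decide entry.

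The cost is a sentence or two in 8.2.4, one form field if it is not already there, and one table. No new assessment is needed, since participants are already asked and concerns already probed and noted. The downside is more non-serious forms (0 to 21 more participants for fatigue, stress and anxiety under the assumed 10% rate, plus any other unrelated AEs), some abstraction from study records, and a by-arm table that is imprecise.

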8.2.5 MULTI-SITE ADVERSE EVENT REPORTING

For this study, only related adverse events will be reported. Adverse events will be reported to U-M IRBMED and NINR using the standard IRBMED reporting schedule: (<https://az.research.umich.edu/medschool/guidance/adverse-event-reporting>). The U-M IRBMED reporting schedule is dependent on the severity of the event, and whether such adverse events were expected. Any serious adverse events will be reported to the ISM, U-M IRBMED and NINR as soon as possible but not later than 7 days of learning of the event. Non-threatening potentially serious adverse events that are causally related to the research will be reported within 14 days of learning of the event to the ISM, U-M IRBMED and NINR.

Sites will report study-related adverse events using the adverse event form in the REDCap study database promptly. In the case of a serious adverse event, the project PI and project manager should be notified by email or phone as soon as possible but not later than 7 days of learning of the event. Adverse events will be discussed at investigator and project staff meetings.

9 STATISTICAL CONSIDERATIONS

9.1 STATISTICAL HYPOTHESES

Primary Endpoint:

1) We hypothesize greater decreases in caregiver strain will be observed among participants in the JITAI group (relative to the control group) at the end of the 6-month home monitoring period.

Secondary Endpoints:

1) We hypothesize greater decreases in anxiety will be observed among participants in the JITAI group (relative to the control group) at the end of the 6-month home monitoring period.

2) We hypothesize greater decreases in depression will be observed among participants in the JITAI group (relative to the control group) at the end of the 6-month home monitoring period.

9.2 SAMPLE SIZE DETERMINATION

Our initial power calculations were based on the expected difference in change in self-reported TBI-CareQOL Caregiver Strain (from baseline to 6-month follow-up) between the JITAI intervention group and the control group. Using self-reported TBI-CareQOL Caregiver Strain, we expect using a normative T-score, with a standardized mean set at 50 and a standard deviation of 9.66, the minimum detectable difference (MID) for caregiver strain to be in the range of 4-6 points. A sample size of 92 in each group will have 80% power to detect a difference in means of 4.0 assuming that the common standard deviation is 9.66 using a two group t-test with a 0.05 two-sided significance level.

Similar results would be expected for the expected difference in change in self-reported PROMIS Depression (from baseline to 6-month follow-up) between the JITAI intervention group and the control group. Using self-

Depression, we expect score, with a at 52.03 and a 9.79, the minimum (MID) for depression 4-6 points. A sample group will have 80%

Effect sizes (T-metric)	Correlation (ρ)				
	0.40	0.50	0.60	0.70	0.80
5	234	230	198	146	82
10	60	58	50	38	22
15	26	26	22	16	10

reported PROMIS using a normative T-standardized mean set standard deviation of detectable difference to be in the range of size of 95 in each power to detect a

difference in means of 4.0 assuming that the common standard deviation is 9.79 using a two group t-test with a 0.05 two-sided significance level.

Similar results would also be expected for the expected difference in change in self-reported PROMIS Anxiety (from baseline to 6-month follow-up) between the JITAI intervention group and the control group. Using self-reported PROMIS Anxiety, we expect using a normative T-score, with a standardized mean set at 54.8 and a standard deviation of 9.53, the minimum detectable difference (MID) for depression to be in the range of 4-6 points. A sample size of 90 in each group will have 80% power to detect a difference in means of 4.0 assuming that the common standard deviation is 9.53 using a two group t-test with a 0.05 two-sided significance level.

With regard to the exploratory analyses, sample size estimates used the following inputs:³¹ 1) type I error rate (α) = 0.05; 2) the smallest meaningful difference to be detected = (δ); 3) power (γ) = 0.8; 4) we assumed outcome marginal variance (σ^2) is constant over time and 10^2 (according to the T-metric used to score each HRQOL domain); 5) the number of repeated measurements per person (n) = 1 baseline, 8 post-baseline for a total of $n=9$ repeated assessments; and 6) with regard to the correlation structure among the repeated measurements we assumed an exchangeable correlation (ρ) = a range of values 0.4, 0.5, 0.6, 0.7, 0.8. The sample size formula is:

$$N = \frac{4 \left\{ Z_{1-\frac{\alpha}{2}} + Z_{1-\gamma} \right\}^2 \sigma_C^2}{\delta^2}, \text{ where } \sigma_C^2 = \text{Var}(C_i) [1 - \{\text{Corr}(Y_{i0}, C_i)\}^2] = \frac{(1-\rho)\{1+(n-1)\rho\}\sigma^2}{n-1}$$

The **Table** provides the sample sizes needed for different effect sizes (δ) and correlations (ρ) when comparing post-baseline averaged outcomes between JITAI and control groups using an ANCOVA
 NIH Behavioral and Social Intervention Clinical Trial Protocol Template v3.0 - 20180827

method (assumed 15% attrition rate³²⁻³⁴). Thus, the proposed sample size of N=240 care partners is sufficient to detect small, but meaningful effects.

Thus, the proposed sample size comfortably exceeds those required to address the primary and secondary endpoint analyses, and is sufficient to examine the tertiary and exploratory endpoints.

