1 PROTOCOL SUMMARY

1.1 SYNOPSIS

Title: Improving Outcomes for Care Partners of Persons with Traumatic Brain Injury

Grant Number: 2R01NR013658

Study Description: Informal family care partners of persons with traumatic brain injury (TBI) are often faced with considerable physical and emotional stress resulting from their caregiver role. Not surprisingly, this stress is associated with depression, anxiety, fatigue, isolation, sleep disturbance, and physical health problems for the care partner. This is especially problematic since these problems also inadvertently affect health and well-being (i.e., outcomes) of the person with TBI. Given this, there is a need for interventions to improve health-related quality of life (HRQOL) for these care partners. Yet, the time demands of caring for an individual with a TBI, as well as the associated physical and emotional toll, make it difficult for care partners to prioritize their own self-care. Therefore, it is critical that interventions are low burden, and easy to engage in, or else there is little hope that the intervention will improve care partner HRQOL.

This study proposes using the TBI-CareQOL, a newly developed HRQOL measurement system specific to care partners of TBI, to evaluate the effectiveness of a personalized health management behavioral intervention aimed at improving the HRQOL of care partners. This personalized intervention, called the just-in-time adaptive intervention (JITAI), uses physical activity and sleep data collected using a wrist-worn device (i.e., a Fitbit®) and real-time self-reports of HRQOL (caregiver strain, anxiety and depression) collected via a mobile app, to provide personalized feedback via app alert.

Participants in this study will be randomized either to a control group, where they will wear the Fitbit® and provide daily reports of HRQOL over a six-month (180 day) period (without the personalized feedback), or the JITAI group, where they will wear the Fitbit®, provide daily reports of HRQOL and receive personalized pushes for 6 months. Up to 280 participants will be enrolled; 140 in the control group and 140 in the JITAI group.

We hypothesize that the care partners who receive the intervention (JITAI group) will show improvements in caregiver strain and mental health (depression and anxiety) after the 6-month (180 day) home monitoring period.

Objectives:

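### Section 9.2 uses the single-time SD of the T-score as the SD of change, so its 80% power rests on an unstated baseline-to-day-180 correlation of 0.5

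*Combined protocol and SAP*

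**What the plan says.** Section 9.2 defines the quantity being powered: "Our initial power calculations were based on the expected difference in change in self-reported TBI-CareQOL Caregiver Strain (from baseline to 6-month follow-up", compared between the two arms. It introduces the spread as "using a normative T-score, with a standardized mean set at 50 and a standard deviation of 9.66", and then carries the same value into the test, "assuming that the common standard deviation is 9.66 using a two group t-test with a 0.05 two-sided significance level". The result is "A sample size of 92 in each group will have 80% power to detect a difference in means of 4.0". Depression (mean 52.03, SD 9.79, 95 per arm) and anxiety (mean 54.8, SD 9.53, 90 per arm) follow the same pattern. None of the three calculations gives an SD of change or a correlation between baseline and day 180.

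Correlations appear only in the exploratory repeated-measures calculation later in 9.2, as "a range of values 0.4, 0.5, 0.6, 0.7, 0.8", together with constant variance over time and 15% attrition. That part cites N=240 and is followed by the statement "Thus, the proposed sample size comfortably exceeds those required to address the primary and secondary endpoint analyses". The current enrolment in section 1.1 is larger: "Up to 280 participants will be enrolled; 140 in the control group and 140 in the JITAI group".

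On analysis, section 9.4.1 names the two-group t-test for inference. Sections 9.4.2 and 9.4.3 compare change between arms and then add a linear mixed model that includes the baseline score as a covariate.

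**The concern.** A t-test on change needs the SD of change, which depends on how strongly day-180 scores correlate with baseline. Putting the score SD in its place fixes that correlation at 0.5 without saying so. A reader cannot tell whether this was intended, and the stated power is right for the planned test only to the extent that 0.5 is. A lower correlation gives less than 80% power at 92 per arm, and a higher one gives more. The same substitution affects both secondary endpoints.

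What is at stake is whether the stated power describes the planned test, and whether the sample size stays adequate over plausible correlations.

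**Working it through.** **Inputs.** From section 9.2: difference 4.0 points; SDs 9.66, 9.79 and 9.53; two-sided alpha 0.05; power 80%. Enrolment is 240 (section 9.2) or up to 280 (section 1.1), allocated 1:1. Three further inputs are assumptions here, because 9.2 gives them only for the exploratory calculation: rho from 0.4 to 0.8, equal variance at both times, and 15% attrition.

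**Step 1: reproduce the plan's figures.** By the normal approximation, n per arm = 2(1.960 + 0.842)² SD² / 4.0².
- Strain: 2 × 7.849 × 9.66² / 16 = 91.6, rounded up to 92.
- Depression: with 9.79, 94.03, rounded up to 95.
- Anxiety: with 9.53, 89.1, rounded up to 90.

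All three match. An exact noncentral-t calculation needs one more per arm (93, 96, 91), and at 92 per arm it gives 79.8% for strain. The powers below are exact-t.

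**Step 2: SD of change.** With equal variances, SD of change = SD × √(2(1 − rho)). This equals the score SD when 2(1 − rho) = 1, that is, at rho = 0.5. At rho 0.4 it is 9.66 × √1.2 = 10.58.

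**Step 3: power for strain, unadjusted t-test on change.** Evaluable per arm is 240 × 0.85 / 2 = 102 and 280 × 0.85 / 2 = 119.

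| rho | SD of change | n per arm for 80% | Power at 92 | Power at 102 | Power at 119 |
|---|---|---|---|---|---|
| 0.4 | 10.58 | 111 | 72.2% | 76.6% | 82.7% |
| 0.5 | 9.66 | 93 | 79.8% | 83.7% | 88.9% |
| 0.6 | 8.64 | 75 | 87.8% | 90.8% | 94.5% |
| 0.7 | 7.48 | 56 | 95.0% | 96.7% | 98.4% |
| 0.8 | 6.11 | 38 | 99.3% | 99.6% | 99.9% |

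The lowest rho that still gives 80% is about 0.50 at 92 per arm, 0.45 at 102 and 0.36 at 119.

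**Step 4: secondary endpoints at rho 0.4.** Depression needs 114 per arm, with 75.5% power at 102 and 81.7% at 119. Anxiety needs 108 per arm, with 77.7% at 102 and 83.7% at 119.

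**Step 5: baseline-adjusted comparison.** For the single day-180 value adjusted for baseline, residual SD = SD × √(1 − rho²), which never exceeds the score SD. At rho 0.4 it is 9.66 × √0.84 = 8.85. Power for strain is then 86.2% at 92 per arm, 89.5% at 102 and 93.5% at 119. The gain from adjustment at rho 0.4 is 76.6% to 89.5% at 102 per arm, and 82.7% to 93.5% at 119.

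**The case against.** The strongest defence is that nothing in the design has to change. The stated sample sizes follow from the stated inputs, so there is no slip of arithmetic. Enrolment is now up to 280, well above 2 × 92 = 184. Section 7.1 replaces participants who leave before the end of home monitoring, so taking 15% off 240 does not describe the current plan; 120 evaluable per arm gives 83.1% at rho 0.4. The mixed model in 9.4.2 already adjusts for baseline, and for a baseline-adjusted comparison the score SD is a conservative choice. All of this stands, and it limits the consequence.

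Three stronger readings are tempting, and the documents do not support them.
- A reader might infer that 80% power holds at a correlation of 0.5 and at no other value. Power rises with rho, so for 92 per arm 0.5 is a lower limit.
- A reader might infer that the primary calculation contradicts the plan's own correlation range. That range belongs to a different analysis (the average of eight post-baseline values, SD 10, ANCOVA), and 0.5 is one of its listed values.
- A reader might infer that the claim of a comfortable margin is false. For strain, power falls short within 0.4 to 0.8 only when four conditions coincide: rho 0.4, an unadjusted change score, the superseded N=240, and 15% attrition without replacement. Even then it is 76.6%.

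The defence does not remove the unstated assumption. Section 9.4.1 makes the t-test the inferential test, and 9.4.2 offers the adjusted model only as an addition, so the power of that model cannot stand in for the power of the planned test.

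**Conclusion.** The point holds as an unstated assumption that should be made explicit. Section 9.2 treats the score SD as the SD of change for all three endpoints, which amounts to rho = 0.5. Over rho 0.4 to 0.8, true power for strain at 92 per arm runs from 72% to 99%, against the stated 80%.

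The current ceiling of 280 enrolled absorbs this. After 15% attrition, power at rho 0.4 is 82.7% for strain, 81.7% for depression and 83.7% for anxiety. Because 280 is a maximum, the margin depends on coming close to it if rho is 0.4 and losses are 15%: strain needs 111 / 0.85, or 131 per arm (262 in all), and depression 114 / 0.85, or 135 per arm (270 in all).

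These figures rest on equal variances at baseline and day 180, on a correlation range and attrition rate borrowed from the exploratory calculation, and, for the adjusted figures, on the single day-180 value instead of the full mixed model. The documents give no estimate of the actual correlation for the primary comparison.

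**What to change.** Restate the primary and secondary calculations in section 9.2 with the current enrolment in place of 240. Give the SD of change as SD × √(2(1 − rho)) over a stated range of rho, and say what attrition is assumed and how replacement enters.

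Preferably, base the power on a baseline-adjusted comparison at day 180, with residual SD = SD × √(1 − rho²). Name that comparison in 9.4.1, 9.4.2 and 9.4.3 as the primary test for each endpoint, in place of the unadjusted t-test on change. The baseline covariate is already in the planned mixed model, so this changes which analysis carries the inference and needs no new data.

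The cost is a rewritten paragraph in 9.2 and a short edit in 9.4. If the change-score test is kept, the stated power at 92 per arm becomes a range that starts lower, at 72% for rho 0.4. No extra enrolment is needed.
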